[USE THIS BIOMEDICAL PROTOCOL TEMPLATE IF YOUR PROJECT INVOLVES ANY PHYSICAL CONTACT OR MEDICAL INTERVENTIONS WITH PARTICIPANTS]

INSTRUCTIONS:

- Depending on the nature of your research, some sections may not be applicable to your research. These sections can be removed as needed.
- When you write a protocol, keep an electronic copy. You will need to modify this copy when making changes.

PROTOCOL TITLE:

Treatment of Stress-Related Psychopathology: Targeting Maladaptive and Adaptive Event Processing

PRINCIPAL INVESTIGATOR:

*[name]
Psychological Sciences
[contact]
[contact]*

UH FACULTY ADVISOR:

If the principal investigator's primary role at UH is resident, fellow or student, identify a faculty advisor.

N/A

OTHER DEPARTMENTS INVOLVED IN THIS STUDY (IF APPLICABLE):

N/A

VERSION NUMBER:

Include the version number of this protocol if assigned by an outside entity.

N/A

DATE:

12/14/2021

Objectives

Directions: Describe the purpose, specific aims or objectives. Be sure to also include the hypothesis being tested

Positive Processes and Transition to Health (PATH) includes six, 90-min sessions that target maladaptive event processing (unproductive processing, avoidance, and impaired reward sensitivity), while also promoting parallel adaptive event processing (constructive processing, approach, and reward seeking) for destabilizing life events and for positive events. PATH uses a platform of narrative revisiting of destabilizing life events, as well as positive life event reminiscence. Patients will be selected for having experienced a destabilizing life stressor and related psychopathology. The R61 trial ($N = 45$) will examine whether PATH engages the therapeutic targets, with clear Go/No Go rules. In the R33, patients ($N = 135$) will be randomized to PATH or progressive muscle relaxation (PMR) and assessed over a 3-month follow-up.

The Specific Aims are:

Specific Aim 1: Engage Therapeutic Targets (R61): In an open trial ($N = 45$), we will examine whether PATH changes therapeutic targets (unproductive processing, avoidance, impaired reward processing) from pre- to 3-month follow-up, with at least medium effects ($d = 0.60$) on two of three primary target measures and at least ($d = 0.50$) on one secondary target measure. We will examine dosing and timing of effects.

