Potentially eligible individuals will complete their informed consent in-person before starting intake (see below for COVID-19 changes). Participants will be informed that participation is optional and that they may discontinue participation at any time. Participants will be provided with the contact information for study staff and the Human Subjects division.

COVID-19 CHANGES

Potentially eligible individuals will complete their informed consent via REDCap, while an assessor is on Zoom with them. Assessors will provide participants with the same information as above. Consent forms have been uploaded that reflect changes to an online and remote intervention and assessments. Assessors will also ask about collecting emergency contact information, in case it's ever needed.

Sharing of Results with Research Participants

Directions: Describe whether results (study results or individual subject results such as results of investigational diagnostic tests, genetic tests, or incidental findings) will be shared with the research participants or others (e.g. the subject's primary care physicians) and if so, describe how the results will be shared.

- Results will not be shared with research participants
- Results will not be shared with research participants' doctors

Study Design

Directions: Describe and explain the overall study design. (eg: single visit, single-blind, double-blind, non-randomized, randomized, blood draw, investigational drug, device etc.)

[figure not shown]
Open Trial of PATH: Engage the Targets (R61)

The R61 will be an open trial to determine if Positive Processes and Transition to Health (PATH) engages the proposed targets: unproductive processing, avoidance, and reward deficits in a *sample of 45 adults* who have experienced a destabilizing life event involving profound loss or threat, report persistent stressor-related symptoms of PTSD and/or depression, and are elevated on symptoms related to 2 of the 3 therapeutic targets. Patients will receive six 90 minute sessions of PATH (with 2 boosters, if partial responders). Primary targets will be assessed at pre-treatment, week 3, post-treatment, and at 1- and 3-month follow-up; secondary targets at pre-treatment, weekly during treatment, post-treatment, and at 1- and 3-month follow-ups. If GO criteria are achieved (Table 3), we will proceed to the R33.

RCT of PATH: Target Engagement and Link to Clinical Outcomes (R33)

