Data will be screened for accuracy, missing values, and fit with the assumptions of GLMM (e.g., linearity, multivariate normality; Tabachnick & Fidell, 2007). Data transformations or model re-specifications will be performed, if needed. Outcome data will be plotted against time to guide selection of applicable time variables; similarly, covariance matrices will be examined to inform selection of the best covariance structure. Best fitting models will be evaluated based on these plots and model fit information (e.g., AIC, BIC). We will use pattern-mixture models to examine whether missingness can be considered ignorable. For non-ignorable missing data, values will be multiply imputed and data recombined (Rubin, 1987) in the mixed model program or comparable model-supported approaches. We will examine associations between primary dependent variables with factors such as gender and time since event and make appropriate adjustments (e.g., covarying predictors). In analyses nesting subjects within treatments (Aim 2), dummy codes will be used (Snijders, 2005).

Power Analysis

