Our approach to power analyses aims to balance pragmatic factors with analytic considerations. We focus primarily on Specific Aim 1 (R61) and Specific Aim 2 (R33). Primary analyses for both aims will involve random effects models; however, because it is difficult to accurately estimate covariance structures of such models, *a priori* power or sample size estimations have limited value. Fang (2006) has shown that ideal sample sizes often far exceed clinical resources for conventional trials, whereas other studies have shown that small sample sizes do not bias estimates of fixed effects (e.g., Bell et al., 2008). Accordingly, we frame our power calculations in line with GLM models that mirror the primary tests and hypotheses of our more complex random effects/GLMM models. In general, estimates were calculated based on $\alpha = .05$ and power $(1 - \beta) = .80$, using intent-to-treat, repeated-measures designs (e.g., paired t-tests). Power calculations were completed using G*Power (Faul et al., 2007). For Aim 1, with an estimated pre-post effect size of $d = 0.60$ (one-tailed tests), we are well-powered with a sample of 45. In fact, for a sample size of 45, an alpha of .05, and power of .80, we will be able to detect a small to moderate effect size of .38. For Aim 2, we based power estimates on a primary comparison of time by treatment interaction in an RMANOVA model. For a five time points, two groups, RMANOVA with a correlation of $r = .70$

between measures, we are well powered to detect treatment X time small effect size of .07 with 67 patients per treatment. For Specific Aim 3, using Monte Carlo simulations in MPlus 6.0 (Muthen & Muthen, 2002) with the same alpha, power, and sample size of at least 67 per condition, we are adequately powered to detect an indirect effect size as small as $d = .50$.

Specific Aim 1: Engage Targets (R61)

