We will examine whether PATH alters therapeutic targets in comparison to PMR. Primary dependent variables are Affective Updating, BATs, PRT. Secondary dependent variables are PTCI, BADS, and SHAPS. We will compare the main effect of treatment (PATH or PMR) over time separately in each of three models. These models will estimate the effects of treatment on both the level of the target at 3-month follow-up and change over time (slope). Random intercepts and random coefficients for time-varying covariates (e.g., time) will be specified, if the model fit is better than a fixed effects model. For example, $y_{ik} = \beta_0 + \beta_1 \text{Time}_{ik} + \beta_2 \text{Treatment}_{ik} + \beta_3 (\text{Treatment}_{ik} \times \text{Time}_{ik}) + v_{0i} + v_{1i} \text{Time}_{ik} + \epsilon_{ik}$ where Treatment represents a dummy-coded effect (Group = 0 for PATH, 1 for PMR), i=subject, k=time, and y = DV of interest. We hypothesize that differences will emerge between PATH and PMR specifically for Affect Updating, BAT, and PRT. For secondary measures, we will use the GLM approach above in an ANCOVA-like design to test the interaction of treatment and time.

Specific Aim 3: Linking Changes in Targets to Changes in Stressor-related Symptoms (R33):

We will examine whether changes in target mechanisms (pre- to post-) predict improvement in PTSD (PSS-I) and depression (QIDS-C) at pre-, mid, post-, 1-, 3-month follow-up. In GLMs, we will evaluate targets from pre- to post-treatment and at 3-month follow-up, with corresponding metrics to assess change in symptoms (PSS-I, QIDS-C). In the GLMs, treatment will predict changes in symptoms from pre- to post-treatment (controlling for baseline levels) and pre- to follow-up. GLMMs will be conducted as above, and treatment will be used to predict levels and change in symptoms. Next, in GLMs, we will

predict pre-post change in target mediators (unproductive processing, avoidance, reward deficits) from treatment (A path) and follow-up outcomes from the mediator (B path), controlling for treatment and baseline symptoms. GLMM will test for mediation by predicting the mediator at all time points from treatment, and the outcome at all time points from the mediator, controlling for treatment. Similar analyses will be used for secondary measures.

Specific Aim 4: Feasibility and Dropout/Acceptability of PATH Intervention (R61/R33):

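### Aim 2 chooses its time form and random slope by fit on the same R33 data it then tests: the slope test's false-positive rate can rise from about 5% to 8–9%, and the 3-month difference can be misread

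*Combined protocol and SAP*

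**What the plan says.** The General Analytic Strategy allows non-linear transformations of time and then states: "Outcome data will be plotted against time to guide selection of applicable time variables". Covariance structures are also chosen after looking at the data, and "Best fitting models will be evaluated based on these plots and model fit information (e.g., AIC, BIC").

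The Specific Aim 2 section adds: "Random intercepts and random coefficients for time-varying covariates (e.g., time) will be specified, if the model fit is better than a fixed effects model". From the resulting model it takes two treatment effects, the level at 3 months and the slope. Its equation is offered only as an example, so it does not fix the time coding. It includes a free treatment main effect, so pre-treatment means are not held equal.

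The assessments are unequally spaced: "Primary targets will be assessed at pre-treatment, week 3, post-treatment, and at 1- and 3-month follow-up". The R33 follows the same schedule.

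The documents give no candidate list, default form, masked or pooled selection step, sensitivity model or use of R61 data to settle the form. The data monitoring section keeps the investigators blind to results while the trial runs, but does not say how arm is handled when the final model is chosen.

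**The concern.** Two separate things can go wrong.

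First, if candidate codings are compared in models that contain treatment-by-time, the winner tends to be the one that best fits the chance difference between arms. That difference is then tested on the same data as if the coding had been fixed.

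Second, the 3-month level is a point on a fitted curve. Sessions end at post-treatment, so an arm difference may level off or fade afterwards, and the protocol itself lists relapse during follow-up as a possibility. A monotone curve cannot follow a rise and a fall, so it carries part of the post-treatment difference forward to 3 months.

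Aim 2 is stated as change from pre-treatment to 3-month follow-up in a randomised comparison. At stake are the error rate of its slope test and the accuracy of its 3-month estimate.

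**Working it through.** **The plan's own figure.** The Power Analysis takes five visits, two arms and r = .70, and concludes: "we are well powered to detect treatment X time small effect size of .07 with 67 patients per treatment". For a repeated-measures interaction, λ = f²·N·m/(1 − r), with N = 134, m = 5 and df = 4 and 528. The smallest f with 80% power is 0.0734, so .07 is reproduced as a rounded value. At exactly .07, λ = 0.0049 × 134 × 5/0.30 = 10.9 and power is 75.5%. This calculation treats visit as categorical. It says nothing about error after model selection.

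**Inputs for the check.** From the documents: 67 per arm, r = .70, α = .05, five visits. Assumed: a two-sided test (none is stated for Aim 2), complete data, visits at weeks 0, 3, 7, 11 and 19, and four codings (linear, log, square root, and change to week 7 then flat).

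**False positives of the treatment-by-time test.** No true interaction; coding chosen by fit with arms in the model. Three sets of simulations:

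| Shared linear trend, SD over 19 weeks | False positives, % |
|---|---|
| 0 | 7.8, 8.1, 7.9 |
| 0.1 | 7.0, 7.6, 7.0 |
| 0.2 | 5.8, 6.5, 6.1 |
| 0.4 | 5.4, 5.2, 5.7 |
| 0.6 | 5.0 (one set) |

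- Coding chosen on data pooled over arms: 4.6–5.4% throughout.
- A further run with no trend gave 9.1%.
- With weeks 0, 3, 6, 10.3 and 19 and a flat mean, two candidate codings gave 6.8–6.9% and five gave 8.2–8.5%. Adding small to moderate random slopes gave 6.2–8.1% and 6.8–9.6%.
- With the model fixed in advance, the rate was 4.7–5.3%.

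**Random slope kept only if fit improves.** By BIC, 6.4–7.0% when slopes vary by 0.3–0.5 SD over 19 weeks. By AIC, 4.9–5.7% for slope SDs of 0.2–0.8.

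**3-month level read off a curve.** With balanced data and equal correlations, the expected fitted difference is the least-squares fit to the true differences: level = d̄ + (Sxy/Sxx)(x₁₉ − x̄). Let the difference rise in a straight line to 0.40 SD at week 7.

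- *Plateau at 0.40, straight line.* d = (0, 0.171, 0.40, 0.40, 0.40), d̄ = 0.274. For weeks, mean 8 and Sxx = 220. Sxy = −0.857 − 0.40 + 1.20 + 4.40 = 4.343. Level = 0.274 + 11 × 4.343/220 = 0.49. The flat-after-week-7 coding returns 0.40 exactly.
- *Half faded, straight decline to 0.20.* d = (0, 0.171, 0.40, 0.333, 0.20), d̄ = 0.221. Straight line: Sxy = −0.857 − 0.40 + 1.00 + 2.20 = 1.943, level = 0.221 + 11 × 1.943/220 = 0.32.
- *Fully faded, straight decline to 0.* d = (0, 0.171, 0.40, 0.267, 0), d̄ = 0.168. Flat-after-week-7 coding: x = (0, 3, 7, 7, 7), mean 4.8, Sxx = 40.8, Sxy = −0.309 + 0.880 + 0.587 = 1.158. Level = 0.168 + 2.2 × 1.158/40.8 = 0.23. Straight line: Sxy = −0.857 − 0.40 + 0.80 = −0.457, level = 0.168 − 11 × 0.457/220 = 0.145.

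When fit picks the coding, simulation gives 0.40–0.48 for the 0.40 plateau, 0.31–0.33 for a true 0.20, and 0.21–0.23 for a true 0.

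**The case against.** **The inflation may be small in practice.** The R33 starts only if at least two of three primary targets change by d ≥ 0.60 in the R61. If PMR patients changed as much, the shared trend would be 0.60 SD, or 0.60 × √(2 × 0.30) = 0.46 SD if d is scaled to the change score. Simulated trends of 0.46–0.60 SD gave 5.2–5.9%. This stands for those targets. But the rule lets one target stay flat, and an open-trial change may not carry over in full.

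**The plan does not say that arms will be visible.** It plots outcomes against time, not by arm. A reader might infer an unmasked choice; the documents are silent, and pooled selection would be harmless for the slope test. Silence still leaves the harmful route open.

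**A single inflated rate, such as 5.5–8%, is tempting but unsupported.** The rate depends on the codings, trend, covariance and selection step, none of which the plan supplies.

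**So is the straight-line result.** A reader might take 0.49 for a true 0.40, or the 11% rejection rate found when a fully faded difference was read off a line, as what the plan will produce. The plan allows curves, and choosing by fit gives 0.40–0.48 for the plateau. Holding pre-treatment means equal would cut the straight-line bias to about 0.02 SD or less, but the plan does not do this, and that relief was shown only for the straight line.

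**Random-slope inflation** appears under BIC and largely disappears under AIC. The plan names both, so it is not an established fault.

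**Status of the trial.** Aim 2 is titled as a replication of target engagement and names both slope and 3-month level, so it would be too strong to call the 3-month level its only endpoint.

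**Conclusion.** The point holds in a limited form. The plan does choose time coding, transformation and random slope from the R33 outcomes it then tests, with no default and no masked step. If arms are in the models being compared, the treatment-by-time false-positive rate is about 5% with a clear shared trend and about 8–9% with little or none, given r = .70, complete data and the assumed codings and weeks. Masked, pooled selection keeps it near 5%.

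The 3-month misreading is separate and does not depend on arms being visible. It is about 0.11–0.13 SD for a true 0.20, about 0.21–0.23 SD for a true 0, and 0 to 0.08 SD for a plateau at 0.40. It rests on the assumed pattern of rise and fade, and would be absent if the chosen curve matched the true one.

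This should be corrected, but it does not undermine the design.

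**What to change.** Before any R33 outcome is seen by arm, state that:

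1. The 3-month PATH–PMR effect in Aim 2 is a contrast from a model with visit as a five-level factor and unstructured covariance. This matches the planned pre-to-follow-up contrast in Aim 1 and the five-visit basis of the Aim 2 power figure.
2. If a time curve is kept for the slope test, its form is fixed in advance, or chosen on data pooled over arms with labels masked.
3. The random slope is kept by default, with a stated fallback for non-convergence. Other time forms are sensitivity analyses.

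The change is to analysis wording only. The cost is power for the 3-month contrast if the difference truly grows in a straight line to 0.40 SD (67 per arm, r = .70, no dropout):

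- Change contrast: SE = √(2 × 0.60/67) = 0.134, z = 2.99, power 85%.
- With baseline adjustment: SE = √(2 × 0.51/67) = 0.123, z = 3.24, power 90%.
- Linear slope: SE = √(2 × 0.30/(67 × 220)) = 0.00638 per week against 0.40/19 = 0.0211, z = 3.30, power 91%.

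Masked selection avoids that loss for the slope test but does not by itself cure the 3-month misreading, so item 1 is needed either way.

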Specific Aim 2: Replication of Target Engagement (R33): In a randomized control trial ($N = 135$), we will examine whether PATH alters therapeutic targets from pre- to 3-month follow-up in comparison to PMR.

Specific Aim 3: Link Changes in Targets to Changes in Stressor-related Outcomes (R33): We will examine whether changes in therapeutic targets (pre- to post-) predict improvement in PTSD and depression symptoms (pre- to 3-month follow-up).

Specific Aim 4: Feasibility and Dropout/Acceptability of PATH (R61/R33): We will examine whether patients perceive PATH as helpful and complete/adhere to treatment, and therapist fidelity.

There is an urgent need to develop novel treatments, given the prevalence, impact, and cost of PTSD and MDD (e.g., Hoge & Chard, 2018). PATH is an innovative intervention that targets three interrelated, transdiagnostic processes that maintain stressor-related psychopathology. PATH's unique early and sustained focus on positive emotions could improve adherence and outcome, particularly in those with the reward deficits commonly seen in PTSD and MDD. Further, PATH's focus on positive emotions and "stuck" processing targets unique processes largely absent in current PTSD therapeutics. PATH is novel in applying exposure principles to depression, not just PTSD. This brief, positive, mechanistically precise, transdiagnostic treatment has the potential to improve treatment engagement and outcomes, identify clear therapeutic targets that predict better outcomes, and ultimately reduce the costly burden of stressor-related psychopathology.

We hypothesize that (1) those in PATH will have significant changes in the therapeutic targets, (2) those in PATH will show a greater change in therapeutic targets than those receiving Progressive Muscle Relaxation (PMR), (3) changes in therapeutic targets predict improvement in PTSD and depression symptoms, and (4) those in PATH will perceive the intervention as helpful and adhere to treatment.

Background

Directions: Describe the relevant prior experience and gaps in current knowledge describing how it will add to existing knowledge. Include any relevant preliminary data.

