Treatment dropout, defined as completing fewer than 4 sessions. Homework adherence between sessions will be assessed using a modified version of the Utility of Techniques Inventory (UTI, Foa et al., 1999). As is standard in many cognitive and behavioral treatment approaches, therapists will also complete an in-session record of client engagement/adherence; specifically, therapists will complete the Negative Event Revisiting Recording Form, on which they record clients' subjective units of distress (SUDs) every 5 minutes while clients engage in the negative event revisiting exercise during sessions 2 through 6. Similarly, therapists will complete the Positive Event Reminiscence Recording Form, on which they record clients' subjective units of pleasure (SUPs) every 5 minutes while clients engage in the negative event revisiting exercise during sessions 2 through 6. Treatment credibility (Treatment Credibility Scale, CS, Addis & Carpenter, 1999) and client satisfaction (Client Satisfaction Questionnaire, CSQ-8; Attkisson & Greenfield, 1994; 2004) will also be assessed. Finally, therapist adherence will be rated via independent rater using a to-be-developed checklist based on a random subset of 10% session recordings.

Milestones (Go/No Go Criteria)

Go/No Go Criteria. For "Go" to be achieved and to proceed to the R33, two criteria must be met. See Table 3. The first is that at least 2 of the 3 primary targets must change. A moderate effect size ($d = 0.60$) was chosen to reflect evidence of clinically meaningful target engagement (see Gold et al., 2017), in line with NIMH guidelines for a preliminary signal of target engagement/efficacy in intervention trials.

Table 3. Target Mechanism Engagement

Phase	Target Mechanism/Outcome	Primary Indicator	Secondary (self-report) Indicator	Go/No Go ¹ Pre-Post Effect Size (Cohen's d)
R61	Unproductive Processing	Affective Updating Task		$d \geq 0.60$
			Posttraumatic Cognitions Inventory	$d \geq 0.50$
	Avoidance	Idiographic Behavioral Approach Task		$d \geq 0.60$
			Behavioral Activation for Depression Scale	$d \geq 0.50$
	Reward Deficit	Probabilistic Reward Task		$d \geq 0.60$
			Snaith-Hamilton Pleasure Scale	$d \geq 0.50$
R33	Posttraumatic Stress Severity	PTSD Symptom Scale-Interview		$d \geq 0.80$
	Depression Severity	Quick Inventory of Depressive Symptomatology-Interview		$d \geq 0.80$

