Note. ¹For Go to R33, at least 2 of the 3 primary mechanism indicators must change and at least one of the secondary indicators must change. For

Second, at least one of the secondary measures must show a moderate effect ($d = 0.50$) from pre- to post-treatment. We included measures of each of the targets, as they are conceptualized as interrelated parts of a "stuck" system. For "Go" to an R01 after the R33, in addition to target engagement, primary outcomes of PTSD and depression must show clinically meaningful gains (e.g., Barth et al., 2016; Cusak et al., 2016).

R33 PATH Refinement. Beyond examining outcome data from the R61, we will: 1) conduct interviews with standardized questions with 20% of patients, selecting those with small and large gains on therapeutic targets; 2) conduct a feedback session with therapists to identify aspects of the manual that need refinement; and 3) examine booster session data regarding whether additional sessions are needed for the R33. The interview guides will be submitted as through a modification before they are conducted.

Data Analysis Plan

Directions: Describe the data analysis plan, including any statistical procedures. If applicable, provide a power analysis, describe primary and secondary study endpoints including safety endpoints.

General Analytic Strategy

For Specific Aims 1–3, we will use random effects models, a specific application of general linear mixed models (GLMMs) that helps to address common issues with longitudinal clinical treatment data, including missingness, serial correlation, and time-varying covariates (e.g., Gallop & Tasca, 2009). These models allow for person-specific deviations from overall mean time effects and are robust to missing data, using maximum likelihood estimation in cases of ignorable non-response. This analytic approach allows for initial modeling of different covariance structures, as well as non-linear time transformations that are especially useful when between-assessment intervals are not consistent across time. For Aim 3, mediation will be tested using the product of coefficients method with bootstrapped standard errors (MacKinnon, 2009) and based on a lagged mediation design (e.g., Hofmann, 2006). This approach addresses the need for temporal precedence of predictor to outcome and accounts for change between time points of a target DV. Analyses involving secondary metrics (i.e., PTCI, BADS, SHAPS) will shift to a more conservative GLM framework.

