We will examine whether PATH engages targets with at least medium-size effects ($d = 0.60$) on 2 of 3 of primary targets from pre- to post-intervention. Primary target dependent variables are: Affective Updating, BAT, and PRT. We will conduct a planned contrast of pre- and follow-up time points within each separate model. This test is analogous to a contrast in ANOVA or a paired t-test, but superior in terms of estimation of missing data and modeling of covariates. The resulting test yields an effect size that can be converted to a d (Feingold, 2013) and compared to our target threshold of $d = 0.60$ for all three models as part of our Go/No-Go rules. For secondary measures of PTCI, BADS, and SHAPS, we will use the GLM approach described above and compare to our target threshold of $d = 0.50$ as part of our Go/No-Go rules.

Dosing and timing of treatment effects. Dosing will be assessed by graphing individual symptom trajectories to identify groups of individuals who may need more treatment, including specifically the shift of positive and negative affect over time (PANAS). To understand timing of effects, primary analyses will be augmented with tests focused on brief, critical change intervals, yoked to the introduction of new target-related content (session k). We will compare residualized change in target (primary measures: Affective Updating, BATs, PRT) in the pre-introduction phase (session k-1 to session k) to change in the post introduction phase (session k+1 to session k+2). These windows will differ for each target, as they are introduced sequentially (e.g., reward deficits, pre-introduction = session 1 and 2, post-introduction = session 3 and 4). Change scores will be compared using t-tests. Similar analyses will be utilized with the PANAS.

Specific Aim 2: Replication of Target Engagement (R33)

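### The power stated for Aim 1 is for showing d > 0 on one measure; Aim 1's own 2-of-3 criterion is met only about 51% of the time at the planning effect of d = 0.60

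*Combined protocol and SAP*

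**What the plan says.** The Power Analysis section (Data Analysis Plan) bases its calculations on alpha .05, power .80 and designs such as the paired t-test, chosen as simpler stand-ins for the primary mixed-model tests. For Aim 1 it states: "For Aim 1, with an estimated pre-post effect size of $d = 0.60$ (one-tailed tests), we are well-powered with a sample of 45". With 45 patients, alpha .05 and power .80, it adds, "we will be able to detect a small to moderate effect size of .38".

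The criterion for Aim 1 is set elsewhere:

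- Objectives, Specific Aim 1, asks whether PATH changes the targets "with at least medium effects ($d = 0.60$) on two of three primary target measures", together with d = 0.50 on one secondary measure.
- Milestones (Go/No Go Criteria): "The first is that at least 2 of the 3 primary targets must change". Table 3 puts d ≥ 0.60 against each primary indicator. The text then adds that "at least one of the secondary measures must show a moderate effect ($d = 0.50$) from pre- to post-treatment".
- The analysis section for Aim 1 (R61) in the Data Analysis Plan repeats the rule: "We will examine whether PATH engages targets with at least medium-size effects ($d = 0.60$) on 2 of 3 of primary targets". The effect size from each model is converted to d and "compared to our target threshold of $d = 0.60$ for all three models as part of our Go/No-Go rules".

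The first hypothesis in the Objectives is worded differently, as a matter of significance: "those in PATH will have significant changes in the therapeutic targets". No section gives the probability of meeting the Go rule at any true effect.

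**The concern.** A reader of the power paragraph would take it that, if PATH works as planned at d = 0.60, Aim 1 will very probably succeed. That does not follow. The calculation asks whether one measure differs from zero. The criterion asks whether the estimates on at least two of three measures reach 0.60, which is the same value the plan assumes to be true. An estimate compared with its own true value falls above it about half the time.

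The 2-of-3 rule decides Aim 1 and is part of what opens the R33. The team, the monitoring board and the funder should therefore know its pass probability before the decision. The detectable .38 is offered as reassurance, yet at that effect the rule would almost always fail.

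**Working it through.** **Inputs from the documents.** N = 45, single arm; one-tailed alpha .05; power .80; planning d = 0.60; Go cutoffs 0.60 (two of three primaries) and 0.50 (one of three secondaries).

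**Assumptions.** d = mean change / SD of change; normal data; full N; correlations of 0 to .9 among measures, since none is given. The documents vary between post-treatment and 3-month follow-up as the endpoint; this does not alter the calculation.

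**Step 1: reproduce the plan's figures.** Let F be the noncentral t distribution function with 44 df and noncentrality δ√45, where √45 = 6.708. Power against d = 0 is 1 − F(1.680).

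- Detectable δ at 80% power: 0.3765, which rounds to the stated .38. A two-tailed test would give 0.427, so the stated figure is the one-tailed, single-measure test.
- Power: .806 at .38, .951 at .50, .990 at .60.
- Smallest observed d that is significant: 1.680 / 6.708 = 0.250.

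**Step 2: chance that one estimate reaches 0.60.** p = 1 − F(0.60 × 6.708) = 1 − F(4.025). At δ = 0.60, p = .509.

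**Step 3: two of three.** With independent targets the probability is 3p²(1 − p) + p³. At p = .5088 this is .381 + .132 = .513. Correlated targets were simulated.

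| True d on all three | Power, one test of d > 0 | P(one estimate ≥ 0.60) | 2 of 3, independent | 2 of 3, correlation .5 | 2 of 3, correlation .9 |
|---|---|---|---|---|---|
| .38 | .81 | .09 | .02 | .06 | .08 |
| .50 | .95 | .28 | .19 | .24 | .27 |
| .60 | .99 | .51 | .51 | .51 | .51 |
| .70 | > .99 | .74 | .83 | .78 | .75 |
| .80 | > .99 | .90 | .97 | .93 | .90 |

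**Step 4: sample size.** At true d = 0.60 with independent targets, the 2-of-3 probability is .516 at n = 30, .513 at n = 45 and .503 at n = 1000.

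**Step 5: the secondary condition.** If the true secondary d is 0.50, one estimate reaches 0.50 with probability .507, and at least one of three does so with probability 1 − (1 − .507)³ = .880. With primaries at 0.60 and all measures independent, the full rule passes with probability .513 × .880 = .45. Correlations up to .5 raise this to about .47. If the true secondary d is 0.80 (the document cites 0.80 for the PTCI and .86 for the BADS), the condition costs almost nothing and the full rule stays at .51.

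**Step 6: sensitivity.**

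- Loss of 20% (n = 36), independent targets: .515 at 0.60 and .81 at 0.70.
- Small-sample correction to d: about .48 at 0.60.
- d on the baseline SD with pre-post r = .70 (the correlation used for Aim 2): .51 to .52 at 0.60 and .83 to .88 at 0.70, for correlations 0 to .5.
- The power figures also move with the standardiser. With equal SDs at both times, d on the baseline SD is divided by √(2(1 − r)) to reach the change-score scale. At r = .3 the divisor is √1.4 = 1.183, and power is 96% at 0.60 and 68% at .38. At r = .70 it is √0.6 = 0.775, and power is about 100% and 94%.

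**Step 7: precision at the cutoff.** An observed d of exactly 0.60 with n = 45 has a 95% interval of 0.28 to 0.91 (inversion of the noncentral t).

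**The case against.** The strongest reply is that nothing in the power paragraph is miscalculated. Its figures are right for the test described, that test fits the first hypothesis, and the milestones are set out in a separate section. The paragraph also warns that a priori power has limited value for mixed models. A Go milestone need not be powered as a hypothesis test. A bar of 0.60 exists to stop treatments whose true effect is .38 or 0.50, so failing there is intended. An observed d between 0.25 and 0.60 that is significant yet misses the Go bar shows two different standards, not a contradiction. And if true effects are 0.80 on all three targets, the rule passes 90% to 97% of the time.

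Most of this stands, and it limits the point. What does not stand is the label. The paragraph attaches its figures to Aim 1, and Aim 1 is defined by the 0.60 threshold on two of three targets. The warning about mixed models concerns covariance structures, not a cutoff on an observed effect. The planning effect is the plan's own 0.60, not 0.80.

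It might also be said that the milestone wording, which asks only that targets change, means statistical significance. Two of three would then pass more than 99.9% of the time at true d = 0.60. Table 3 and the Specific Aim 1 analysis section both set a numeric threshold, so that reading is not supported.

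**Conclusion.** The Aim 1 power statement is wrong as written: it gives the power of a one-measure test against zero as though it were the power for Aim 1. At the planning effect on all three targets, that test has 99% power, while the 2-of-3 part of the criterion is met about 51% of the time. The 51% is stable to correlations of 0 to .9 and to 20% loss. It stays between about .48 and .52 across the forms of d tried. The probabilities at other true effects depend more on the correlations and on the standardiser, neither of which the plan fixes.

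A reader might infer that the arithmetic is mistaken, that 45 patients are too few, or that 0.60 is the wrong milestone. The documents support none of these. The .38 reproduces. The chance at 0.60 stays near one half from n = 30 to n = 1000. The milestone is a deliberate choice, explained in the Milestones section as marking clinically meaningful engagement. Nor is the Go decision a coin toss in general: it is one only when true effects sit at the cutoff.

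**What to change.** Keep N = 45 and the 0.60 milestone. Replace the Aim 1 power sentences with wording such as:

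> With N = 45 and d defined as mean change / SD of change, a one-tailed paired t-test on one measure has 99% power to show d > 0 at a true d of 0.60 and 80% at .38. These figures do not describe the Go rule. If the true d is equal on all three primary targets (assumed correlations 0 to .9 among measures, full N), the 2-of-3 criterion is met with probability about 0.51 at 0.60, 0.75–0.83 at 0.70 and 0.90–0.97 at 0.80. The secondary condition can lower this somewhat: to about 0.45–0.47 at primary d = 0.60 if true secondary effects are only 0.50 (correlations 0 to .5).

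In the Specific Aim 1 analysis section, state the standardiser used in the conversion to d and whether a small-sample correction applies. Use the same d in the power sentence and recompute both sets of figures if it is not the SD of change. Put the team's own correlations in place of the assumed ones if it has them. Report each d with its confidence interval beside the Go decision.

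The cost is wording and reporting only. The one drawback is a less favourable stated chance of success.
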